#### 7.3 Pregnancy and Breastfeeding

If a participant becomes pregnant during the study, she may choose to continue study-provided medications during pregnancy and breastfeeding, after discussion with her primary clinician and the A5290 CMC, given the lack of optimal alternatives for TB treatment in the setting of a PI-based ART regimen. Participants who choose to continue all study-provided medications will be followed on study through the completion of the

pregnancy and the outcome of the pregnancy will be recorded on the CRF. If a participant chooses not to continue either study-provided anti-TB or antiretroviral medications, she will be referred to local clinics and will receive the best available TB or ART as determined by her primary clinician, but will continue to be followed on study but off study-provided anti-TB or antiretroviral medications, or both, and the outcome of the pregnancy will be recorded on the CRF.

If a woman has completed the study or chooses to discontinue from the study before the end of the pregnancy, the site staff should request permission to contact her regarding pregnancy outcomes at the end of the pregnancy. If the information is obtained, pregnancy outcomes will be submitted on a CRF at the end of the pregnancy. A5290 will not provide prenatal or postpartum care to infants born to women on study through the protocol; however, women who become pregnant on study will continue to be followed as described above but will be referred to local clinics and/or other research studies for prenatal and postpartum care.

Pregnancies that occur on study will be reported to The Antiretroviral Pregnancy Registry. Intrapartum complications and/or pregnancy outcome will be recorded on the CRFs and also reported to The Antiretroviral Pregnancy Registry. More information is available at [www.apregistry.com](http://www.apregistry.com). [contact]; [contact].

## 8.0 CRITERIA FOR DISCONTINUATION

### 8.1 Permanent ARV Treatment Discontinuation

- Drug-related toxicity (see section 7.1).
- Requirement for prohibited concomitant medications (see section 5.4).
- Stopping the last component of study-provided ART.
- Request by participant to terminate treatment.
- Clinical reasons believed life threatening by the physician, even if not addressed in the toxicity section of the protocol.

NOTE: Participants must be referred to their primary care clinician/clinical facility or ART program and treated with the best available ART if they permanently discontinue study-provided ARVs.

### 8.2 Permanent TB Treatment Discontinuation

- Qualifying episode of suspected TB determined not to be TB.
- Drug-related toxicity (see section 7.1).
- Requirement for prohibited concomitant medications (see section 5.4).
- Stopping the study-provided TB drug.
- Completion of TB treatment as defined in the protocol.
- Request by participant to terminate treatment.
- Clinical reasons believed life threatening by the physician, even if not addressed in the toxicity section of the protocol.

NOTE: Participants must be referred to their primary care clinician/clinical facility or TB program and treated with the best available TB treatment if they permanently discontinue study-provided anti-TB treatment.

### 8.3 Premature Study Discontinuation

- Failure by the participant to attend 3 consecutive clinic visits.
- RIF resistance found after study entry.
- Request by the participant to withdraw.
- Request of the primary care provider if he/she thinks the study is no longer in the best interest of the participant.
- Participant judged by the investigator to be at significant risk of failing to comply with the provisions of the protocol as to cause harm to self or seriously interfere with the validity of the study results.
- At the discretion of the ACTG, institutional review board (IRB)/ethics committee (EC), US Food and Drug Administration (FDA), Office for Human Research Protections (OHRP), NIAID, investigator, pharmaceutical supporter(s), or local governmental authorities.

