#### 4.2 Exclusion Criteria

- 4.2.1 History of completed TB treatment and resolution of TB symptoms less than 1 year prior to the current TB episode at study entry, or incomplete treatment for a prior episode of TB (i.e., defaulted past TB treatment) at any time prior to the current TB episode.

NOTE: Completed TB treatment is defined as completion of an 8-week intensive phase of TB treatment with INH and RIF plus at least 2 other anti-TB drugs, followed by a 16-week continuation phase of TB treatment with INH and RIF for a total duration of at least 24 weeks of TB treatment.

- 4.2.2 Documented multidrug-resistant tuberculosis (MDR TB) or extensively drug-resistant (XDR) TB.

NOTE: MDR TB is defined as TB with resistance to RIF and INH. XDR TB is defined as MDR TB plus resistance to fluoroquinolones and to at least one second-line injectable anti-TB drug. If MDR TB or XDR TB is determined based on locally-obtained drug susceptibility testing after study entry, the participants will be discontinued from the study and referred to their primary clinician/clinical facility or TB and ART program and treated with the best available TB and ART according to local standards of care.

- 4.2.3 Participants infected with a rifamycin resistant strain of TB as determined by HAIN GenoType MTBDR Plus line probe assay or, GeneXpert® MTB/RIF assay (or, following approval of the core team, a result from another locally-obtained standardized RIF drug susceptibility test). Participants found to have a rifamycin-resistant strain of TB should be referred for management according to the site's standard of care.

NOTE A: Participants may be enrolled pending the results of RIF drug susceptibility testing if a rapid HAIN GenoType MTBDR Plus line probe

assay, GeneXpert® MTB/RIF assay, or other rapid MTB RIF drug resistance assay result is not yet available. However, if RIF drug-susceptibility test results are not available within 60 days after study entry or if any drug susceptibility testing subsequently demonstrates RIF resistance, participants will be discontinued from the study and referred to their primary clinician/clinical facility or TB and ART program and treated with the best available TB and ART according to local standards of care.

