**Premature ARV and/or TB Treatment and Premature Discontinuation Evaluations**

Participants who prematurely discontinue from the study, and participants who prematurely discontinue ARV and/or TB treatment, will have the discontinuation evaluations performed as noted in the SOE within 4 weeks after the discontinuation. If the participant discontinues any study-provided ARV, he/she will continue on the remaining study-provided ARVs and the date of the discontinuation of any study-provided (or study treatment) ARV drug and reason for discontinuation will be entered on the Antiretroviral Regimen Record. If the participant discontinues any study-provided TB drug, he/she will continue on the remaining TB drugs and the date of the discontinuation of the study-provided (or study treatment) TB drug and the reason for discontinuation will be entered on the TB Treatment Record.

When the participant takes the last dose of the last study-provided (or study treatment) drug (ARV and/or TB drugs), the Permanent Discontinuation of Study Drugs form will be completed with the date of study drug discontinuation and the reason for discontinuation. If the participant discontinues all study-provided (or study treatment) ARV or TB drugs prematurely, he/she will be encouraged to continue on study, off study treatment, and receive all evaluations as per the SOE through week 72.

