#### Entry and Subsequent Sputum Collections

At entry (not required if obtained within 3 days prior to entry), week 8, week 12, and at the time of suspected TB treatment failure/TB recurrence, participants will be given sterile collection containers to collect first morning expectorated sputum the day of their clinic visit. These specimens will be collected by induction if they cannot be spontaneously produced.

Sputum will be collected as described below:

- If the final dose of intensive phase of INH, RIF or RBT, EMB and PZA coincides with the week 8 visit, collect sputum samples within 72 hours of ingestion of the final dose of intensive phase of TB treatment and prior to the ingestion of the second dose of continuation phase TB medications.
- If the final dose of intensive phase INH, RIF or RBT, EMB and PZA does NOT coincide with the week 8 visit, (a) collect a sputum sample at week 8, and (b) schedule a separate visit within 72 hours of ingestion of the final dose of intensive phase of TB treatment and prior to the ingestion of the second dose of continuation phase TB medications.

- From week 16 onward, collect single sputum samples every 4 weeks (monthly) for smear and cultures if sputum culture results have not demonstrated two consecutive TB-negative cultures after week 12, and discontinue monthly smear and cultures once there are two consecutive TB-negative sputum cultures. Drug susceptibility testing on available samples should be done if the sputum culture remains MTB positive after the week 8 timepoint.

If the sputum sample does not become TB-negative by the week 16 time point, the participant has failed TB treatment. The participant will be taken off study TB medications and will be treated for possible drug-resistant TB at the discretion of the primary clinician according to local, national, or international guidelines used for treatment of drug-resistant TB. These participants will be followed on study, but off study-provided TB drugs until week 72. If the participant must discontinue study-provided TB treatment, he/she may still continue to take study-provided ARVs.

Collect sputum in a sterile single-use collection container. If possible, the oral cavity should be rinsed with clean water that is expectorated prior to giving the sample. The specimen should contain 3-5 mL of sputum.

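### The rule withdrawing participants for rifampin (RIF) resistance found after entry is not limited to the entry isolate, and for resistant week-16 TB failures it conflicts with the rule that keeps them on study to week 72

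*Protocol*

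**What the plan says.** **Leave the study.** Protocol 8.3 gives, among the reasons for premature study discontinuation, "RIF resistance found after study entry". Note A to exclusion criterion 4.2.3 says that "if any drug susceptibility testing subsequently demonstrates RIF resistance, participants will be discontinued from the study". The April 2013 clarification memo rewrites Note A (item 1) but keeps that clause. The note to 4.2.2 likewise takes participants off study if local testing after entry shows MDR or XDR TB, both of which include RIF resistance. None of these is tied to the entry isolate or limited in time.

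**Stay on study.** Section 6.3.2 (Entry and Subsequent Sputum Collections) calls for testing of later isolates: "Drug susceptibility testing on available samples should be done if the sputum culture remains MTB positive after the week 8 timepoint". It then states: "If the sputum sample does not become TB-negative by the week 16 time point, the participant has failed TB treatment". Such participants stop study TB medication and are treated for possible drug-resistant TB at the clinician's discretion. Their follow-up is explicit: "These participants will be followed on study, but off study-provided TB drugs until week 72". No exception is made for RIF resistance.

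**Text on intent.** Section 6.3.5 (TB Evaluations) ties discontinuation to the qualifying episode proving drug-resistant. Section 9.4.2 allows 3% for resistance present at entry, but the sentence before it takes off study anyone found after enrollment to have a RIF-resistant isolate.

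**Scoring.** Section 9.6.2 counts participants without virologic data as not suppressed.

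**The concern.** Resistance already present at entry is an eligibility matter, and removing those participants is defensible. Resistance that emerges on treatment is different: it is an outcome of the randomised regimen. Protocol 2.1 says, tentatively, that low rifabutin exposure appears to be associated with acquired rifamycin resistance, so the frequency could differ between the rifabutin arms (A and C) and the RIF arm (B).

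If 8.3 is applied to acquired resistance, the participant's later HIV RNA, TB and safety follow-up is lost, and a missing week-48 HIV RNA becomes a virologic failure. A TB event is thus recorded as an HIV event, possibly unequally by arm. If 6.3.2 is applied instead, the same participant contributes data to week 72. Sites following different sections would handle identical cases differently.

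**Working it through.** **1. The instructions side by side**

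| Situation | 8.3, 4.2.3 Note A, 4.2.2 note | 6.3.2 |
|---|---|---|
| Entry isolate found RIF-resistant after enrolment | Leave study | Not addressed as such |
| Week-16 failure, isolate RIF-susceptible | Not triggered | Stay to week 72, off study TB drugs |
| Week-16 failure, later isolate RIF-resistant | Leave study | Stay to week 72, off study TB drugs |

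Only the third row conflicts. The qualifying-episode wording in 6.3.5 does not settle it, because disease still present at week 16 is arguably the same episode, and 6.3.5 refers back to section 4.0, which contains Note A. Section 9.4.2 does not settle it either, since it speaks both of resistance at entry and of isolates found resistant after enrollment.

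**2. When the week-48 value is lost**

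The discontinuation visit falls within 4 weeks of withdrawal (6.2.7), and visits have a 7-day window (6.2.3). If the week-48 value may come from week 47 onward, it can be captured only when withdrawal is at week 47 − 4 = 43 or later. This treats the visit window as the analysis window; 9.6.2 defines none.

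**3. The plan's own sample size**

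Inputs from 9.4.2: 50% v 70%, two-sided 0.025, 90% power, normal test for two proportions. With pooled null variance and no continuity correction:

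n = [2.2414·√(2·0.6·0.4) + 1.2816·√(0.7·0.3 + 0.5·0.5)]² / 0.20² = 146.7, so 147 per arm.

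Then 147/0.97 = 151.5, so 152; 152/0.97 = 156.7, so 157; and 3 × 157 = 471. All agree with the protocol. Power at 147 is Φ[(0.20·√147 − 2.2414·0.6928)/0.6782] = 90.1%.

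**4. Illustration for acquired resistance**

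The documents give no rate. Assume a proportion q of 1-3% in the rifabutin arm, none in Arm B, and every case withdrawn early enough to lose week 48.

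- *Cases would have been suppressed at the arm average:* the comparison is 0.70(1 − q) v 0.50, and the difference shrinks by 70q points.
- *All cases would have been suppressed (the extreme):* the comparison is (0.70 − q) v 0.50, and the difference shrinks by 100q points.

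| q | Shrinkage, average | Power, n=147 | Shrinkage, extreme | Power, n=147 |
|---|---|---|---|---|
| 1% | 0.7 | 87.6% | 1.0 | 86.4% |
| 2% | 1.4 | 84.7% | 2.0 | 81.9% |
| 3% | 2.1 | 81.4% | 3.0 | 76.7% |

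If both arms had the same q and cases were suppressed at each arm's average, the difference would shrink by 20q = 0.2-0.6 points and power would be 89.3-87.6%.

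**5. At the size actually planned for accrual period 1**

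At 20 per arm (SAP 1.3), expected cases are 20q = 0.2-0.6 per arm. One case moves an arm's suppression rate by up to 1/20 = 5 points.

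**6. Is the resistance endpoint lost?**

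Under 6.3.7, a positive culture after 16 weeks of treatment, in someone documented to be taking TB medication, is already treatment failure, and TB outcome is also recorded at premature discontinuation. So the failure and its resistance result usually count for 1.3.7 and 9.2.3.5 before withdrawal. A case could be missed only if resistance is reported before week 16. That requires a week-8 sample to be cultured, tested and reported in under 56 days, or a week-12 sample in under 28. The only limit given for a susceptibility result applies to entry testing: "if RIF drug-susceptibility test results are not available within 60 days after study entry". At 60 days those samples would report at weeks 16.6 and 20.6, too late to cause the loss. Faster testing would reopen the window.

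**The case against.** The best defence is that only entry resistance was meant. Note A is attached to an entry exclusion criterion, it deals with people enrolled while results are pending, the memo version opens with specimens available at entry, and the 3% allowance in 9.4.2 is for entry resistance. Section 6.3.2 speaks of possible drug-resistant TB, so it could also be read as the default, with 8.3 taking over once RIF resistance is confirmed. Both readings are reasonable, but they send the same participant in opposite directions, and the protocol does not choose. What stands is that the conflict is confined to a small subset.

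A reader might infer more than the documents support:

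- *That 8.3 also contradicts 6.2.7.* That section says of someone who stops all study ARV or TB drugs that "he/she will be encouraged to continue on study, off study treatment, and receive all evaluations as per the SOE through week 72". It names people who leave the study separately and says only that they "will have the discontinuation evaluations performed as noted in the SOE within 4 weeks after the discontinuation". The retention sentence concerns stopping drugs, so it can coexist with 8.3.
- *That the TB resistance endpoint is lost.* It usually is not, as step 6 shows.
- *That the arm-average powers are a floor.* They are not. They depend on what withdrawn participants would otherwise have achieved, and the extreme case is lower.
- *That the primary comparison is at risk.* SAP 1.6 states that accrual period 2 will not open, and the SAP provided contains no week-48 virologic comparison.

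**Conclusion.** The point holds as a minor inconsistency with a small, real consequence. As written, study discontinuation for RIF resistance is not limited to the entry isolate, and for a week-16 failure with a RIF-resistant later isolate it conflicts with 6.3.2, with no rule of precedence. The cost of withdrawal is later HIV RNA, TB and safety follow-up, plus a non-suppressed score at week 48 if that value is missing.

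The effect of 0.7-2.1 points, at most 1-3, rests on an assumed 1-3% acquired-resistance rate in the rifabutin arm only, with every case withdrawn before week-48 data. It describes a comparison at a size that will not be reached. No confirmatory conclusion depends on it. What remains is descriptive follow-up of accrual period 1 participants, where fewer than one case per arm is expected at the assumed rates.

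**What to change.** By clarification memo, amend 8.3, 4.2.3 Note A and the 4.2.2 note, and align the matching sentence in 9.4.2:

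- Limit discontinuation from the study to resistance in the baseline (entry) isolate. Name the isolate explicitly; borrowing the qualifying-episode wording of 6.3.5 would leave the ambiguity in place.
- Keep the 60-day rule for missing entry results unchanged.
- Where the entry isolate was susceptible and a later isolate is resistant, stop study-provided TB drugs, refer for local treatment, and keep the participant on study to week 72 with HIV RNA, TB and safety outcomes collected, as 6.3.2 already does for week-16 failures.

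The 4.2.2 note must be included. Otherwise a later isolate resistant to both RIF and isoniazid would still trigger withdrawal and the conflict would survive.

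The cost is one memo item; the sponsor has already used a memo to edit Note A. The downside is that a few participants keep scheduled visits while receiving TB care locally.

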## 9.0 STATISTICAL CONSIDERATIONS

### 9.1 General Design Issues

This is an open-label, randomized, phase 2b study to evaluate whether a standard dose lopinavir/ritonavir (LPV/r) regimen, with or without raltegravir (RAL), coupled with rifabutin (RBT)-based TB treatment is superior to a double dose LPV/r regimen coupled with rifampin (RIF)-based TB treatment. We intend to recruit 471 HIV-infected participants with active TB who require protease inhibitor (PI)-based antiretroviral therapy (ART). Each participant will be followed until week 72. We anticipate accrual to occur at the rate of approximately 4-5 participants per month per site once all sites are registered and enrolling participants.

### 9.2 Primary Endpoints

#### 9.2.1 Accrual Period 1 PK Study Endpoints

- 9.2.1.1 LPV plasma concentrations at day  $12 \pm 2$  (after initiation of ART) in Arms A, B, and C.
- 9.2.1.2 RBT plasma concentrations at day  $12 \pm 2$  (after initiation of ART) in Arms A and C.
- 9.2.1.3 Grade 3 or 4 laboratory value or sign or symptom attributed to study-provided medication(s) by 28 days of ART.

9.2.1.4 Discontinuation of study-provided drug(s) for treatment-limiting toxicity or intolerance (such that PK assessments within the day  $12 \pm 2$  (after initiation of ART) window cannot be completed).

9.2.2 Primary endpoint: HIV virologic suppression is defined as plasma HIV-1 RNA level  $< 400$  copies/mL at 48 weeks.

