C	LPV 400 mg/RTV 100 mg tabs BID + two NRTIs + RAL 400 mg BID	INH 300 mg daily, RBT 300 mg daily, then 150 mg daily upon initiation of ART*, EMB (weight-based dose) daily, PZA (weight-based dose) daily, and pyridoxine 25 mg daily. EMB and PZA will be discontinued after 8 weeks of treatment; INH, RBT 150 mg daily (or the adjusted dose determined by PK), and pyridoxine will continue for a minimum total duration of 24 weeks. INH, RBT, and pyridoxine may continue beyond the 24 weeks to a maximum of 48 weeks at the discretion of the primary clinician; the protocol core team must be notified.	LPV/r + two NRTIs + RAL will continue at standard dosing through week 72	This regimen follows the same rationale as for Arm A but adds RAL in an attempt to enhance the antiviral activity of LPV/r when combined with RBT to evaluate whether this approach is associated with a better virologic response than the other two arms.

\*NOTE: In Arms A and C, RBT should be administered at a dose of 300 mg daily until the start of antiretroviral therapy at which time the dose should be reduced to the 150 mg daily dose. If LPV/r is stopped prematurely during TB treatment, the RBT dose should be increased to 300 mg daily and the team should be notified. All participants will receive TB treatment according to in-country TB guidelines for daily TB treatment and directly observed therapy (DOT), except that all study participants will receive daily TB treatment 7 days per week, i.e., participants will not use a 5 days per week schedule that may be recommended in some in-country TB programs.

Accrual will take place in two accrual periods. Accrual period 1 will enroll participants who will undergo an initial dose-finding period before continuing regular study follow-up through 72 weeks. Once review of the dose-finding data in accrual period 1 is completed, accrual period 2 will begin.

#### Accrual Period 1

Sixty participants will be randomized 1:1:1 (20 participants per arm) to one of three treatment arms as detailed above. Anti-TB therapy with study-provided RBT or non-study-provided RIF and non-study-provided INH, EMB, and PZA should be started within 72 hours of randomization. ART should be started as soon as possible after initiating anti-TB therapy, but may be delayed for up to 7-14 days after starting anti-TB therapy to allow participants sufficient time to assess tolerability of TB medications. Participants will then undergo a formal PK and safety evaluation to include:

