### 5.0 STUDY TREATMENT

#### 5.1 Regimens, Administration, and Duration

##### 5.1.1 For Participants Enrolled During Accrual Period 1

At entry, participants will be randomized (1:1:1) to one of the following three arms: Arm A, Arm B, and Arm C as further defined in this section. Anti-TB therapy with study-provided RBT or non-study-provided RIF and non-study-provided INH, EMB, and PZA should be started within 72 hours of randomization. ART should be started as soon as possible after initiating anti-TB therapy, but may be delayed for up to 7-14 days after initiation of anti-TB therapy to allow for assessment of initial tolerability of TB medications.

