#### 5.1.4 Duration

ART will continue through week 72 after study entry. Anti-TB treatment will continue for a minimum total duration of 24 weeks to a maximum of 48 weeks as specified by the participant's local primary clinician.

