\* If the participant has exclusively extrapulmonary TB and sputum cannot be induced, a sputum sample is not required, but a specimen from any clinically relevant extrapulmonary site, if available (e.g., pleural, pericardial, or peritoneal fluid or tissue biopsy; aspirate of lymph node, cold abscess, bone marrow or joint fluid; cerebrospinal fluid; liver, bone marrow or other tissue biopsy or; blood) should be submitted for AFB smear, mycobacterial culture, and TB drug susceptibility testing (see section 6.2.6). Drug susceptibility results for both RIF and INH should be recorded when available.

\*\* The pregnancy test must be negative within 7 days prior to study entry and 72 hours of starting study medications.

\*\*\*Unless the week 2 or week 4 visit did not take place, the full Clinical Assessment does not need to be conducted. If the week 2 visit or week 4 visit did take place, only the vital signs and weight need to be collected.

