### 6.2.3 Post-Entry Evaluations

Study visits must be scheduled  $\pm$  7 days of the weeks indicated in the Schedule of Events (SOE). There should be no study visits after the week 72 (final study) visit.

NOTE: The PK visit on day 12 (after initiation of ART) has a window of  $\pm$  2 days, and therefore, could be combined with the week 2 or 4 visit.

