### PK and Safety Criteria

- For RBT (Arms A and C), equivalence analyses will compare day  $12 \pm 2$  (after initiation of ART) RBT 24-hour AUC and  $C_{max}$  with control data derived from prior PK studies, as determined by whether the 90% confidence intervals of the ratios of the RBT concentrations (when co-administered with LPV/r) relative to daily RBT concentrations in the absence of LPV/r are fully contained within the pre-specified NEB of 67%-150%. RBT concentrations in Arms A and C will be judged acceptable if equivalence is declared according to these PK parameters.
- For LPV in Arm B, the primary PK parameter is the day  $12 \pm 2$  (after initiation of ART)  $C_{min}$  ( $C_{12}$ ), and the acceptable lower limit value is  $\geq 1$  mg/L. LPV concentrations in Arm B will be judged acceptable if no more than three participants have a  $C_{min} < 1$  mg/L.
- No more than three participants in any treatment arm experience a Grade 3 or Grade 4 AE attributable to study-provided medication by 28 days after ART initiation.
- No more than three participants in any treatment arm discontinue study-provided drug(s) for treatment-limiting toxicity or intolerance (such that PK assessments within the day  $12 \pm 2$  (after initiation of ART) window cannot be completed).

The justification behind the RBT PK criterion is given in section 9.4.1. The other three criteria depend on the number of events (i.e., no more than 3). Based on Table 9.2 below, supposing the underlying rate is 10%, with  $X=3$ , there is an 87% chance of the study regimen in a particular arm going forward to accrual period 2.

Table 9.2. Probability (%) of Deciding the Criterion is Acceptable Based on a Range of Underlying Rates

Underlying Rate	Probability of X or Fewer Events in 20 Participants Given the Underlying Toxicity Rate:				
	X=1	X=2	X=3	X=4	X=5
0.05	0.736	0.925	0.984	0.997	0.999
0.10	0.392	0.677	0.867	0.957	0.989
0.15	0.176	0.405	0.648	0.830	0.933
0.20	0.069	0.206	0.411	0.630	0.804
0.25	0.024	0.091	0.225	0.415	0.617

The core team will also examine the LPV concentrations in Arms A and C in order to determine if RBT affects LPV concentrations. Any dose modifications of

LPV in Arms A and C will be the guided by the modifications proposed for Arm B (see Table 5.1 in section 5.1.1).

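### The accrual period 1 safety criterion closes 28 days after ART start, but safety visits are timed from study entry, so with delayed ART the last part of the window has no scheduled safety visit

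*Protocol*

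**What the plan says.** **Criterion.** Protocol 9.2.1.3 sets the endpoint as "Grade 3 or 4 laboratory value or sign or symptom attributed to study-provided medication(s) by 28 days of ART". Under PK and Safety Criteria in 9.5.1, an arm passes if no more than three participants have a Grade 3 or 4 event "attributable to study-provided medication by 28 days after ART initiation". SAP 1.5.2 anchors the same 28 days to the start of study-provided ART and TB medications. If that means the later of the two starts, it is the same clock.

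**Start of treatment.** Protocol 3.0 says that anti-TB therapy "should be started within 72 hours of randomization". ART is to follow as soon as possible, "but may be delayed for up to 7-14 days after starting anti-TB therapy"; 5.1.1 repeats this.

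**Visits.** Study weeks count from entry (5.1.4: "ART will continue through week 72 after study entry"). Section 6.2.3 schedules visits within ± "7 days of the weeks indicated in the Schedule of Events (SOE"), and the first columns are weeks 2, 4 and 8. The only visit tied to ART start is the PK visit at ART day 12 ± 2. Section 6.2.3 lets it be combined with week 2 or week 4. If either of those visits took place, the footnote to 6.1 says that "only the vital signs and weight need to be collected" at the PK visit.

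**Allowance for delayed ART.** Section 9.5.1 recognises that ART may be delayed and times the PK assessments from ART start for that reason. It makes no matching provision for safety visits.

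**The concern.** The endpoint follows one clock and the visits that supply its data follow another. When ART is delayed, the window closes some time after the last scheduled safety visit inside it, and the next visit is too late to count.

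This matters most for laboratory events. A symptom can be reported at the next visit with its onset date. An asymptomatic rise in transaminases or fall in neutrophils is dated by the blood draw. If it resolves before week 8 it is never seen. If it persists, SAP 4.1 places it in the table of events beyond 28 days, outside Safety Criterion #1. The protocol gives reason to expect such events: section 2.1 describes a study of 21 adults on double-dose LPV/r with RIF in which two had asymptomatic Grade 3 or 4 transaminase elevations, and it discusses neutropenia with RBT.

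A participant lost before day 28 counts as a failure (9.6.1), but one who stays in the study and has no late test counts as event-free. The error therefore runs towards passing an arm.

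**Working it through.** **Step 1. The plan's own figure.** Table 9.2 gives the probability of three or fewer events in 20 participants. Exact binomial, P(X ≤ 3 | n = 20, p):
- p = 0.10: 0.867 (table: 0.867)
- p = 0.15: 0.648 (table: 0.648)
- p = 0.20: 0.411 (table: 0.411)

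The table is right. It assumes that every event is detected.

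**Step 2. Range of ART start.** Let s be the study day of ART start. TB treatment starts on day 0 to 3 and ART 0 to 14 days later, so s runs from 0 to 3 + 14 = 17.

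**Step 3. Visits on the ART clock.** ART day of a visit = study day − s. Week 4 is nominally study day 28 (window 21 to 35). Week 8 opens on study day 56 − 7 = 49. Days from nominal week 4 to ART day 28 = 28 − (28 − s) = s. If week 4 is held on study day 21, the gap is 28 − (21 − s) = s + 7. If it is held on study day 35, the gap is s − 7, or zero if that is negative.

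| s | Nominal week 4 (ART day) | Week 4 window (ART days) | Week 8 opens (ART day) | Uncovered days, nominal | Week 4 early | Week 4 late |
|---|---|---|---|---|---|---|
| 0 | 28 | 21 to 35 | 49 | 0 | 7 | 0 |
| 3 | 25 | 18 to 32 | 46 | 3 | 10 | 0 |
| 7 | 21 | 14 to 28 | 42 | 7 | 14 | 0 |
| 10 | 18 | 11 to 25 | 39 | 10 | 17 | 3 |
| 13 | 15 | 8 to 22 | 36 | 13 | 20 | 6 |
| 14 | 14 | 7 to 21 | 35 | 14 | 21 | 7 |
| 17 | 11 | 4 to 18 | 32 | 17 | 24 | 10 |

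Week 8 is never inside the window, because its earliest ART day is 49 − 17 = 32. The PK visit falls on ART days 10 to 14, so it does not shorten the tail below 14 days. If it is combined with week 4, which the windows allow for s = 7 to 17, the tail is at least 14 days.

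**Step 4. Effect on the criterion (assumptions, not document figures).** Take a true rate of 20%, a constant hazard over the 28 days, week 4 on its nominal date and all events laboratory-only. The missed share for a participant is then s/28.
- Full detection: P(pass) = 0.411.
- ART starts spread evenly over days 0 to 14: mean s = 7, missed 7/28 = 25%, effective rate 0.20 × 0.75 = 0.15, P(pass) = 0.648.
- Everyone starts on day 14: missed 14/28 = 50%, effective rate 0.10, P(pass) = 0.867.
- Everyone starts on day 7 and only half of events are laboratory-only: missed 0.5 × 7/28 = 12.5%, effective rate 0.175, P(pass) = 0.526.

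**Step 5. Which laboratory tests fall where.** As the Schedule of Events reads in the text available, liver tests are marked at weeks 2 and 8 but not week 4, and hematology and chemistries are marked at week 4. The column alignment is not reliable, so this must be checked against the original table. If it is right, the gap for liver tests is wider than the one above: with s = 14 to 17, nominal week 2 is ART day 0 or earlier and nominal week 8 is ART day 39 to 42.

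**The case against.** A reader might infer that, whenever ART is delayed, no visit falls in the second half of the window. The documents do not support that. For starts on study days 7 to 13, nominal week 4 falls on ART days 21 to 15, inside the second half. It falls before ART day 14 on nominal dates only for starts on days 15 to 17, and even then a late week 4 visit can reach the second half. ART is also to start as soon as possible, so the two-week delay is the permitted extreme.

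A reader might also take the rise from 0.41 to 0.87 as the expected effect. It needs every participant in the arm to start on day 14, every event to be laboratory-only, and none of the late half to be counted. The endpoint includes signs and symptoms, and 6.3.5 has each visit cover what happened since the last one. The case with everyone delayed seven days and half of events laboratory-only gives 0.53.

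Other review exists. The core team sees unblinded event reports weekly (9.5.1), safety trends can trigger an early SMC review, and SAP 4.1 tabulates events beyond 28 days. These limit the harm, but they see only what was collected, and later events stay outside the criterion.

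Last, SAP 1.6 states that accrual period 2 will not open, so no arm can now advance wrongly. That stands. SAP section 6 nevertheless requires the report to say whether the safety criteria were acceptable, so the count still needs to be interpretable.

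**Conclusion.** The mismatch is real and follows from the visit weeks alone. With ART started on study day s, the last s days of the 28-day window have no nominal safety visit: 7 days at s = 7, 14 to 17 at the permitted maximum, and up to 24 if week 4 is held early. Participants who start ART within about three days of entry lose little on nominal dates, provided that the relevant tests are done at week 4.

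The direction is towards under-counting asymptomatic laboratory events. The size cannot be derived, because the documents give neither the distribution of ART start nor the share of events that are laboratory-only. At an assumed true rate of 20%, P(pass) moves from 0.41 to 0.65 if a quarter of events are missed; 0.87 is the upper extreme. Whether liver tests have a wider gap depends on the original Schedule of Events.

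**What to change.** **Protocol 6.1 and 6.2.3, accrual period 1.** When ART is delayed, hold the week 4 safety visit at ART day 28 (±3 days), with hematology, liver tests and chemistries. Have the existing day 12 ± 2 PK visit then carry the full clinical assessment and the same safety laboratories. Both parts are needed: with ART on day 14, week 2 falls on ART day 0, so moving week 4 alone would leave no full safety visit before ART day 28. The moved visit does not collide with week 8, since at s = 17 it ends on study day 17 + 28 + 3 = 48 and week 8 opens on day 49.

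**Criterion.** Keep the 28-day limit, allowing for the window of that visit. Do not move week 8 findings into the primary count: for a day-14 start that visit runs to ART day 63 − 14 = 49, which Table 9.2 was not calibrated for.

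**SAP 4.1.** Report by arm how many participants had safety laboratories at or near ART day 28. As a sensitivity analysis, give the count that includes Grade 3 or higher values first found at the next scheduled visit. This part can be done with the data already collected.

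**Cost.** One re-timed visit, and one added set of safety laboratories at a visit where blood is already drawn, in up to 60 participants.
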